**Power Analysis:** Given the developmental nature of this study, our primary objective will be to determine a reasonable effect size for the SHE intervention for planning a future randomized trial, rather than to determine statistical significance between groups. Sample size requirements were estimated based on having adequate power to find clinically meaningful effects of the intervention on each of the primary outcomes, including reducing the percent of participants who screen positive for the health risk of PTSD, while also acknowledging the need to maintain a modest sample size in the initial test of a novel treatment approach. As documented below, we determined that an initial sample size of no more than 155 would meet these goals.

Research conducted by Himmelfarb and colleagues (2008) indicated that approximately 60% of VA women who screened positive for MST indicated PTSD. Given that we will identify women not only with MST, but a lifetime ST, we conservatively estimate that 60% of women included in the study will screen positive for PTSD. With an initial sample of no more than 155 women, retaining 126 over the 4-month follow-up, power would be .80 to detect an effect size  $h$  of .53 (equivalent to a medium effect size), with an alpha of .05, over the 4-month follow-up. This would be achieved, for example, with rates of PTSD at follow-up of 34% in the program vs. 60% in control.

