The sample size of no more than 155 women would also be sufficient for detecting changes in the proportion of women indicating an alcohol use problem or occurrence of IPV over the follow-up. Based on findings suggesting that 7-14% of VA women with MST report SUD, and 64% of women with any lifetime sexual abuse report alcohol abuse, we conservatively estimate that 40% of women included in the study will screen positive for alcohol problems. Thus, the sample of no more than 155 accounting for attrition would allow a power of .80 to detect an effect size  $h$  of .44 of changes in alcohol use problems over the follow-up. This would be achieved with rates of alcohol use problems of 20% vs. 40% in control. Further, based on data indicating that 33% of women with a history of sexual victimization are revictimized, 44% of active duty military women report lifetime IPV, and studies indicating that IPV revictimization ranges from 18% to 74% over 6- to 9-month follow-ups (see Kuijpers et al., 2011), we conservatively estimate that 40% of women with a history of lifetime ST presenting at the VA would report lifetime IPV, and 25% would report a revictimization experience over the 4-month follow-up. A sample of no more than 155 accounting for attrition would allow a power of .80 to detect an effect size  $h$  of .46 in changes in IPV revictimization over the 4-month follow-up. This would be achieved with rates of IPV revictimization of 8.5% in the SHE program vs. 25% in the control group.

The sample size of no more than 155 will also be sufficient for detecting changes in the proportion of women who reduce the number of risks over the follow-up. Among the full sample of no more than 155 women, power would be .85 to detect an effect size  $h$  of .44 in any reduction (i.e., 1 to 0 risks, 2 to 1 risk, 3 to 2 risks, etc.) in the number of risks; which would be achieved, for example, with 20% of women in control and 40% of women in SHE reducing the number of risks reported over the follow-up. Power would also be adequate to examine reductions in the number of risks among women experiencing various numbers of risks (i.e., women reporting 1 risk vs. 2. vs. 3). In light of high comorbidity between PTSD, IPV, and

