substance use, we projected that 50 women will report 1 risk, 50 women will report 2 risks, and 50 women will report three risks. Thus, among women reporting each number of risks (i.e., we expect 50 women will report 1 risk), power would be .73 to detect an effect size  $h$  of .64, which would be achieved with 20% of women in the control group reporting a reduction, and 50% of women in SHE reporting a reduction.

**Limitations** The limitations of this study include: potential issues related to disclosure of sensitive information, the use of self-report, assessment reactivity and effect on measured outcomes, the inclusion of only English-speaking participants, generalizability of study results to other Veteran or service member populations, and an inability to meaningfully examine ethnic/racial differences in the proposed sample.

**Revision:** Based upon experience during the Development and Trial Phase, evaluation of the program, and feedback from participants, the Investigator Team will revise the intervention. Information regarding the recruitment methods and retention of participants will be utilized in the design of a later clinical trial. This final revision phase will generate the final “product” of this treatment development study, to be used in the application to evaluate SHE in a large-scale clinical trial.

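### The power section does not say whether alpha .05 is one- or two-sided, its five powers follow no single rule, and two of them ignore the expected attrition

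*Combined protocol and SAP*

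**What the plan says.** All of this is in Section 4, Data Analysis, under Power Analysis.

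- **Purpose.** The aim is to find a reasonable effect size for a later trial, "rather than to determine statistical significance between groups". The same paragraph nevertheless says the sample size was set to give adequate power on the primary outcomes, and offers the calculations that follow as support for 155.
- **Alpha.** It is given once, in the PTSD calculation: "with an alpha of .05, over the 4-month follow-up". One- or two-sided testing is not mentioned there or anywhere else in the document.
- **PTSD.** With up to 155 enrolled and "retaining 126 over the 4-month follow-up, power would be .80 to detect an effect size" h of .53 (34% vs 60%).
- **Alcohol.** "Thus, the sample of no more than 155 accounting for attrition would allow a power of .80 to detect an effect size" h of .44 (20% vs 40%).
- **IPV.** "A sample of no more than 155 accounting for attrition would allow a power of .80 to detect an effect size" h of .46 (8.5% vs 25%).
- **Any reduction in number of risks.** "Among the full sample of no more than 155 women, power would be .85 to detect an effect size" h of .44 (20% vs 40%).
- **Strata by number of risks.** "Power would also be adequate to examine reductions in the number of risks among women experiencing various numbers of risks". The basis is that "we projected that 50 women will report 1 risk, 50 women will report 2 risks, and 50 women will report three risks", and the stated power is .73 for h = .64 (20% vs 50%).

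**The concern.** Two separate problems appear on reading the paragraph.

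First, on Cohen's h scale the power of a two-group comparison depends only on h, the number analysed and alpha. Three outcomes with h of .53, .44 and .46, on what reads as the same retained sample and the same alpha, cannot all have power .80. Because sidedness is missing, the reader cannot tell which figure is off, or in which direction.

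Second, the PTSD, alcohol and IPV powers allow for attrition, while the any-reduction and stratum powers use all enrolled women. Yet a reduction in risks over follow-up can only be seen in women who have follow-up data.

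If testing is two-sided, the alcohol and IPV powers fall short of what is claimed. Under either reading, the any-reduction and stratum powers are too high. The results are meant to feed the design of a larger trial, so unclear power assumptions could be carried forward.

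**Working it through.** **Inputs.** Rates, h values, stated powers, 155 enrolled and 126 retained: Power Analysis. Retention is 126/155 = .813. Equal allocation is inferred from the section on potential benefits, which says half the participants receive no intervention; the randomization text gives no ratio. That alcohol and IPV also rest on 126 women is inferred from their reference to attrition.

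**Effect sizes.** h = |2·arcsin√p1 − 2·arcsin√p2| gives .527 (PTSD), .442 (alcohol and any reduction), .456 (IPV) and .644 (strata). These agree with the stated h values, so the discrepancy lies in the powers.

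**Powers as stated.** Power = Φ(h·√(n/2) − z), with n per arm and z = 1.960 two-sided or 1.645 one-sided. At n = 63, √31.5 = 5.612. For alcohol, .44 × 5.612 = 2.470, giving Φ(0.510) = .695 two-sided and Φ(0.825) = .795 one-sided. All five, using the stated h and each figure's own N:

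| Outcome | h | N | Stated | Two-sided | One-sided |
|---|---|---|---|---|---|
| PTSD | .53 | 126 | .80 | .845 | .908 |
| Alcohol | .44 | 126 | .80 | .695 | .795 |
| IPV | .46 | 126 | .80 | .733 | .826 |
| Any reduction | .44 | 155 | .85 | .782 | .863 |
| Each stratum | .64 | 50 | .73 | .619 | .732 |

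The one-sided rule matches or slightly exceeds the last four but gives .91 for PTSD. The two-sided rule matches none.

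**Other tests.** A pooled two-proportion test on the rates at 63 per arm gives .841, .692 and .703 two-sided and .907, .795 and .804 one-sided (PTSD, alcohol, IPV). Subtracting a continuity correction of 1/n from the difference brings PTSD to .792 two-sided, but takes alcohol to .619 and IPV to .614.

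**Implied alpha.** Setting power to .80 on 126 women, one-sided alpha = 1 − Φ(h·√31.5 − .842), doubled for a two-sided test. The two-sided values are .033 (PTSD), .104 (alcohol) and .082 (IPV). These are three different alphas, and none is .05.

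**Detectable effect.** At power .80 on 126 women, h = (z + .842)/√31.5, which is .499 two-sided and .443 one-sided. For h = .44 at power .80, about 162 women must be analysed two-sided and 128 one-sided.

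**Applying the plan's retention.** Any reduction at 126 women; strata at 50 × 126/155 = 40.6 women each:

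| Outcome | Stated | N after attrition | Two-sided | One-sided |
|---|---|---|---|---|
| Any reduction | .85 | 126 | .695 | .795 |
| Each stratum | .73 | 40.6 | .532 | .654 |

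For any reduction, attrition costs .782 − .695 = .087 two-sided or .863 − .795 = .068 one-sided. The choice of sidedness costs .863 − .782 = .081 at 155 women and .795 − .695 = .100 at 126.

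**The case against.** The strongest reply is about weight. The plan says significance testing is not its main objective, and the overview of Data Analysis promises good power only for effects of roughly medium size. A detectable h of .50 on 126 women, two-sided, is in keeping with that. A one-sided .05 rule also reproduces four of the five figures, and the PTSD figure is then merely conservative. This stands, and it limits the consequence. It does not make the figures right: a one-sided test is never declared, and the section presents these powers as the support for 155.

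A second reply is that 126 is attached only to PTSD, and that two-sided testing on all 155 would give about .78 for alcohol and .79 to .82 for IPV. The shared retained sample is indeed an inference. But using 155 contradicts the plan's statement that those two figures account for attrition, and it still does not yield .85 or .73.

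A third reply is that the analyses use all available data, so a woman seen only at 2 months still contributes. That is fair. It would place the any-reduction power between the values for 126 and 155 women: .70 to .78 two-sided, or .80 to .86 one-sided. Women with no follow-up add nothing. The figure of about 41 women per stratum assumes the same retention at every risk level, which the plan does not state.

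**Conclusion.** The concern holds. Sidedness is not stated, and no single combination of test and alpha reproduces the five powers. If testing is two-sided, alcohol (.70) and IPV (.73) fall short of the claimed .80, while PTSD (.84) exceeds it. If it is one-sided, alcohol and IPV are about as claimed and PTSD (.91) is understated.

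Separately, and under either reading, the any-reduction and stratum powers leave out expected attrition. They fall from the stated .85 to .70 or .80, and from the stated .73 to .53 or .65 (two-sided or one-sided).

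This rests on 1:1 allocation, 126 women for each outcome after attrition, and equal retention across strata. All values are simple two-proportion powers. They are not the power of the baseline-adjusted Poisson GEE specified for the primary outcome. The stated powers should be corrected; the aim of estimating an effect size is not threatened.

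**What to change.** State the sidedness of alpha and the analysed N behind every power, and apply 126/155 retention to every outcome that needs follow-up. Then restate the figures on one basis. Using the stated h values:

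| | Two-sided .05 | One-sided .05 |
|---|---|---|
| PTSD, 126 women | .84 | .91 |
| Alcohol, 126 women | .70 | .80 |
| IPV, 126 women | .73 | .83 |
| Any reduction, 126 women | .70 | .80 |
| Each stratum, about 41 women | .53 | .65 |
| Detectable h at power .80, 126 women | .50 | .44 |

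If 2-month data alone are enough to classify a woman on any reduction, say so and give the range up to the 155-woman value (.78 two-sided, .86 one-sided). Replace the claim of adequate stratum power with a statement that stratum results are exploratory estimates reported with confidence intervals.

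The cost is rewording of the power section, with some figures less favourable than before. Enrolment and the analysis itself do not change.

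### The IPV power of .80 rests on a 25% control rate with no stated denominator and an alpha with no stated sidedness; depending on these, power is about .33 to .73 two-sided or .45 to .82 one-sided

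*Combined protocol and SAP*

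**What the plan says.** All of this is in Section 4, Data Analysis, Power Analysis, unless noted.

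- The IPV inputs for the 4-month follow-up come in one sentence, presented as a conservative estimate: "40% of women with a history of lifetime ST presenting at the VA would report lifetime IPV, and 25% would report a revictimization experience". The supporting sources include "studies indicating that IPV revictimization ranges from 18% to 74" percent over 6 to 9 months, and a 33% revictimization figure for women with a history of sexual victimization.
- The claim follows: "A sample of no more than 155 accounting for attrition would allow a power of .80" for an effect size h "of .46 in changes in IPV revictimization over the 4-month follow-up", illustrated by "rates of IPV revictimization of 8.5% in the SHE program vs. 25% in the control group".
- The retained sample is given in the PTSD calculation: 126 of at most 155. The error rate also appears only there, "with an alpha of .05, over the 4-month follow-up", with no mention of one or two sides.
- The paragraph says the sample is sufficient to detect changes in IPV occurrence. It also says the main objective is to find a reasonable effect size for a later trial rather than to test significance.
- Of the women included, 60% are expected to screen positive for PTSD and 40% for alcohol problems. Fifty women each are projected to have one, two and three risks.

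**The concern.** The 40% and the 25% stand side by side, and the calculation uses only the 25%, applied to everyone retained. If the 25% was meant as a rate among women who have experienced IPV, the control rate in the whole sample is much lower than the one used. If it was meant as a share of all women, it demands a very high rate among those with an IPV history. In neither case does the text support a conservative power of .80 as it stands.

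The Composite Abuse Scale (CAS) is listed as a primary-outcome measure in Table 1, and the plan says the sample was sized for adequate power on each primary outcome. A reader who accepts .80 could take a null IPV result as evidence of no effect when planning the larger trial.

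**Working it through.** **Inputs.** Control 25%, SHE 8.5%; 126 retained; lifetime IPV 40%; cited revictimization range 18% to 74% over 6 to 9 months (all from Power Analysis). Allocation is taken as 1:1, so 63 per arm, because the section on potential benefits says half of participants receive no intervention. Alpha is .05, with both sidedness options tried.

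**Formula.** h = 2·asin(√p1) − 2·asin(√p2). Power = Φ(h·√(n/2) − z), with n per arm and z = 1.960 (two-sided) or 1.645 (one-sided).

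**Step 1: the plan's own figure.** h(.25, .085) = .4555, matching the stated .46.

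- 63 per arm: h·√(63/2) = 2.557. Two-sided power is Φ(0.597) = .725; one-sided is Φ(0.912) = .819.
- A pooled-variance test gives .703 and .804.
- All 155 women (77.5 per arm), two-sided: .809. This contradicts the statement that attrition was allowed for.

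So .80 reproduces one-sided with 126 women, or two-sided with no attrition.

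**Step 2: can the sidedness be inferred?** With 126 women, the alcohol claim (h = .44, stated .80) gives .795 one-sided and .695 two-sided. The 50-women claim (h = .64, stated .73) gives .732 one-sided and .619 two-sided. Both point to one-sided. The PTSD claim (h = .53, stated .80) gives .908 one-sided and .845 two-sided, matching neither. The sidedness cannot be settled from the text.

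**Step 3: 25% as a share of all women.** If all events arise among the 40% with an IPV history, the implied rate there is .25 / .40 = 62.5% in 4 months. That is near the top of a cited range measured over longer follow-up. Power is as in Step 1.

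**Step 4: 25% as a rate among women with an IPV history, share 40%.**

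- Whole sample: control .40 × .25 = 10%; SHE .40 × .085 = 3.4%; h = .2726. With 63 per arm, power is .334 two-sided and .454 one-sided.
- Only women with an IPV history: .40 × 126 = 50.4, or 25.2 per arm; h = .4555. Power is .366 two-sided and .489 one-sided.
- Pooled-variance versions run slightly lower: .31 to .34 two-sided, .43 to .47 one-sided.

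**Step 5: other IPV shares, same conditional reading.** Each range runs from the whole-sample to the subgroup calculation.

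| IPV share | Two-sided | One-sided |
|---|---|---|
| 40% | .33–.37 | .45–.49 |
| 60% | .48–.51 | .60–.63 |
| 80% | .61–.63 | .73–.74 |
| 100% | .72–.73 | .82 |

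Equal groups with one, two and three risks average 2.0 risks per woman. Subtracting the plan's 60% PTSD and 40% alcohol leaves 2.0 − 0.6 − 0.4 = 1.0, an IPV share near 100%. That does not fit with 40%.

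**Step 6: the cited range.** With a 40% share, revictimization of 18% to 74% among women with an IPV history, and the same relative reduction (8.5/25 = .34 of the control rate), power with 63 per arm runs from .25 to .81 two-sided and .36 to .88 one-sided.

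**The case against.** A reader might infer that the true power is simply .33 to .37. The documents do not support that, for four reasons.

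1. The two percentages share one grammatical subject, women with lifetime ST. Read literally, the 25% covers all of them and there is no dilution. The implied 62.5% lies inside the cited range.
2. A reader might also infer that only women with prior IPV can have an event. The CAS outcome is any abuse in the period (Baseline and follow-up assessments of IPV), and all randomized women with a baseline assessment are analysed (Primary outcomes, Aim 4a). A first IPV experience would count. The 33% source also concerns women with sexual victimization, which every participant has.
3. The 40% describes women with ST presenting at the VA. Enrolled women must also have heavy drinking, PTSD or IPV, so their IPV share may be higher.
4. Setting a two-sided .33 against a .80 that reproduces one-sided exaggerates the fall. Like for like, it is .73 to .33–.37 two-sided, or .82 to .45–.49 one-sided. For the same reason, .73 against .80 at face value is an unstated convention, not a proven error.

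It can also be said that the plan puts estimation ahead of significance testing and lists the separate IPV comparison under secondary outcomes.

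All of this stands against a single corrected number. It does not rescue the .80 as written. The literal reading keeps the figure but is hard to reconcile with calling the estimate conservative, and no rate is given for first-time IPV that would ease this. The estimation objective does not make a stated power correct, and the same paragraph still calls the sample sufficient.

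**Conclusion.** The point holds as a problem of undefined and inconsistent inputs. With 126 women retained, the stated .80 needs the 25% to apply across the whole sample and a one-sided test that the plan never mentions; two-sided, it needs no attrition. Power is about .73 two-sided or .82 one-sided if the 25% covers all women, and about .33 to .37 or .45 to .49 if it covers only women with an IPV history and they are 40% of the sample. Intermediate IPV shares fall between.

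These figures assume 1:1 allocation, 63 per arm, alpha .05 and a simple comparison of two proportions. The planned GEE on repeated measures could give somewhat different values.

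**What to change.** In the Power Analysis paragraph:

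- State the denominator of the 25%.
- State the IPV share assumed for the enrolled sample, and reconcile it with the projection of 50 women at each number of risks.
- State whether alpha is one- or two-sided.
- Replace the single .80 with the figure that follows. If the inputs stay open, give the range: about .33 to .73 two-sided, or .45 to .82 one-sided.
- Either justify describing the 25% as conservative or drop that description.
- Remove the statement that the sample is sufficient for IPV, and describe that comparison as effect-size estimation, in line with the paragraph's own objective.

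The cost is protocol wording only; sample size and procedures need not change. The downside is that one stated power becomes less favourable.

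### The number-of-risks power figures (.73 by group, .85 overall) reproduce only one-sided with no attrition, so the claim of adequate by-group power is unsupported, as is the 50/50/50 split beneath it.

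*Combined protocol and SAP*

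**What the plan says.** All of this is in Section 4, Data Analysis, Power Analysis.

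- **Full sample.** Power is given as .85 for h of .44, illustrated by 20% of control women and 40% of SHE women reducing their number of risks.
- **By number of risks.** The plan continues: "Power would also be adequate to examine reductions in the number of risks among women experiencing various numbers of risks". It cites high comorbidity and says "we projected that 50 women will report 1 risk, 50 women will report 2 risks, and 50 women will report three risks". For each group, "power would be .73 to detect an effect size" h of .64, illustrated by 20% vs 50%.
- **Alpha and attrition.** Alpha is .05, stated once, in the PTSD paragraph, without sidedness. That paragraph assumes 126 of at most 155 women are retained to 4 months. The alcohol and IPV figures also allow for loss; for IPV, "A sample of no more than 155 accounting for attrition would allow a power of .80". Neither number-of-risks sentence mentions attrition.
- **Risk rates.** For PTSD, "we conservatively estimate that 60% of women included in the study will screen positive for PTSD". For alcohol, "we conservatively estimate that 40% of women included in the study will screen positive for alcohol problems". For IPV, "we conservatively estimate that 40% of women with a history of lifetime ST presenting at the VA would report lifetime IPV". No rate of 12-month IPV-positive screens among enrolled women is given, although that is the entry criterion in Section 3.

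**The concern.** A stated power can be relied on only if its sidedness and analysed sample size are known. Here neither is given. The two number-of-risks figures sit beside figures that allow for attrition, so a reader will assume that they do too.

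The trial's stated purpose is to plan a larger one. A planner who accepts that power is adequate for women with one, two and three risks may read a null by-group result as informative when it is not, or may carry the equal split into the next design. The full-sample figure matters as well, because the number of risks is the primary outcome.

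The split raises a separate question: whether the section's own prevalence figures lead to equal thirds.

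**Working it through.** **Inputs.** Group size 50, with 20% vs 50%; full sample 150 (the three groups summed) to 155, with 20% vs 40%; alpha .05; retention 126/155 = .813 (all from Power Analysis). Allocation is 1:1, since Potential Benefits says half of the participants receive no intervention. A group of 50 is therefore 25 per arm.

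**Formula.** Cohen's h = 2·arcsin√p₁ − 2·arcsin√p₂. Power = Φ(h·√(N/4) − z), with N the total in both arms and z = 1.645 one-sided or 1.960 two-sided.

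**Step 1: reproduce the .73.** For 20% vs 50%, h = .6435, which the plan rounds to .64.
- One-sided, h = .64, N = 50: .64 × √12.5 = 2.263; Φ(2.263 − 1.645) = Φ(.618) = **.73**. With unrounded h it is .74.
- Two-sided: Φ(2.263 − 1.960) = Φ(.303) = **.62**.

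The plan's figure is therefore one-sided with all 50 women analysed.

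**Step 2: apply the plan's retention.** 50 × 126/155 = 40.6 women. With h = .6435, h·√(40.6/4) = 2.051.
- One-sided: Φ(.406) = **.66**.
- Two-sided: Φ(.091) = **.54**.

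With h rounded to .64 these are .65 and .53.

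**Step 3: size needed for .80**, the level quoted for the individual risks. N = 4·[(z + .842)/.6435]² gives about 60 women analysed one-sided or 76 two-sided. Divided by .813, that is about 74 or 94 enrolled per group, against 50 projected.

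**Step 4: the full-sample .85.** For 20% vs 40%, h = .442 (rounded to .44). Ranges cover both values of h.

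| Women analysed | One-sided | Two-sided |
|---|---|---|
| 150 | .85–.86 | .77 |
| 155 | .86–.87 | .78–.79 |
| 126 | .80 | .69–.70 |

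Again the stated figure needs a one-sided test and no attrition.

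**Step 5: the split.** 50×1 + 50×2 + 50×3 = 300 risks in 150 women, a mean of 2.0. For enrolled women that mean equals the PTSD rate plus the drinking rate plus the IPV rate. With those rates fixed, overlap between risks moves them between women but does not change the sum.
- At 60% and 40%, IPV = 2.0 − .60 − .40 = 1.00. The split is then exactly attainable: 50 IPV only, 40 IPV with PTSD, 10 IPV with alcohol, 50 with all three. PTSD is 40 + 50 = 90 of 150 and alcohol is 10 + 50 = 60 of 150.
- If the five women outside the split (155 − 150) each have one risk, there are 305 risks. PTSD and alcohol supply 155 × 1.0 = 155, so IPV must supply 150 of 155, or 97%.
- The plan's highest alcohol figure is 64% ("of women with any lifetime sexual abuse report alcohol abuse"). With 60% PTSD it still needs IPV = 2.0 − 1.24 = 76%.

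**The case against.** **The risk rates may not describe enrolled women.** Entry requires at least one risk. If 60/40/40 are rates among all women with sexual trauma and 30% of those women have none of the three risks, enrolled rates are .60/.70 = 86%, .40/.70 = 57% and 57%. These sum to 2.0 and allow the split. On that reading the appeal to comorbidity is coherent, because overlap determines how many women qualify. The plan also calls its rates conservative; the alcohol rate is built from substance-use-disorder and alcohol-abuse figures, whereas entry needs one occasion of 4 or more drinks; and advertising in mental health and substance abuse clinics could raise the rates. This stands. A reader might infer that the split is impossible, or might insert the 40% IPV figure as proof. The documents do not support that: the 40% is lifetime IPV among women with sexual trauma presenting at the VA, not 12-month IPV among those enrolled.

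**One-sided testing may be intended.** The hypotheses are directional and no two-sided test is specified. That is fair, but the section does not let a reader infer a one-sided convention. At 126 women the alcohol figure (.80, h of .44) fits one-sided (.80; two-sided .69), while the PTSD figure (.80, h of .53) fits neither version of this formula (.91 and .84). One-sided testing also leaves attrition unaddressed.

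**Retention of .813 is not the only basis.** The plan uses all available data, and the GEE spans 2 and 4 months, so .66 and .54 assume equal retention across groups and analysis of 4-month completers. This is a fair caveat on the replacement figures. It does not rescue .73 as stated.

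**Little depends on it.** The Power Analysis puts effect-size estimation ahead of significance, the baseline count is only a covariate in the primary model, and no test by baseline number of risks is specified. This stands and limits the severity.

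**Conclusion.** The power point holds and needs no assumption about IPV. Both number-of-risks figures depend on an unstated one-sided test and on no loss to follow-up. By group, .73 becomes .62 two-sided, and about .66 one-sided or .54 two-sided after the plan's retention; the adequacy statement is not supported. For the full sample, .85 becomes .77 to .79 two-sided, and about .80 one-sided or .70 two-sided at 126 women. These values rest on the arcsine approximation, 1:1 allocation and, where retention is applied, equal retention and 4-month completers.

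The split point is conditional. Read literally as rates in women included in the study, 60% and 40% require essentially every enrolled woman to be IPV-positive, which the plan nowhere supports. Higher enrolled rates would produce the split. It is an unsupported projection, not an arithmetic contradiction.

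Severity is minor.

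**What to change.** In the Power Analysis:

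1. Restate both number-of-risks figures with their sidedness and the 126/155 retention: about .66 one-sided or .54 two-sided by group, and about .80 or .70 for the full sample. Note the assumptions of equal retention across groups and analysis of 4-month completers. Correcting only the by-group sentence would leave the paragraph inconsistent.
2. Remove or qualify the adequacy statement for the by-group comparisons, and label them exploratory.
3. Give the enrolled PTSD, heavy-drinking and 12-month IPV rates that produce 50/50/50, or say that the split is an assumption.

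The cost is rewording within the Power Analysis and less favourable stated power. Sample size, the primary GEE and data collection do not change.
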